Protocol Number: 20200497

Date: 10FEB2023 Page 1 of 36

Statistical Analysis Plan

Protocol Title:	A Multicenter, Randomized, Double blinded Study Evaluating the Pharmacokinetics, Efficacy, Safety and Immunogenicity of Multiple Switches Between Humira® (adalimumab [US]) and ABP 501 Compared With Continued Use of Adalimumab in Subjects with Moderate to Severe Plaque Psoriasis		
Short Protocol Title:	A Study to Investigate Interchangeability of ABP 501 for the Treatment of Subjects with Moderate to Severe Plaque Psoriasis		
Protocol Number:	20200497		
NCT Number: EudraCT:	NCT05073315 2021-000542-18		
Authors:			
Sponsor:	Amgen Inc. [name]		
SAP Date:	Document Version Current (v2.0)	Date 10FEB2023	

Protocol Number: 20200497

Date: 10FEB2023 Page 2 of 36

Version Number	Date (DDMMMYYYY)	Summary of Major Changes, including rationale
Current (v2.0)	10FEB2023	Updated the definition of the PK Concentration Analysis Set in section 6.3 to clarify that PK samples on or after randomization date should be included. Updated the definition of the PK Parameter Analysis Set in section 6.3 to consist of all randomized subjects who receive at least one IP dose post-randomization from who receive all assigned IP doses post-randomization, and who have an evaluable ABP 501 or Humira serum concentration-time profile between weeks 28 and 30. The Per-protocol PK Parameter Analysis Set was changed accordingly and consists of all subjects in the PK Parameter Analysis Set who do not have an important protocol deviation during the study that could affect the primary PK endpoints. Clarified Lead in Treated Set would be used for all analyses for the Lead-in Period in section 6.7. The previous version mentioned safety analyses and PK concentration summary only. Added PK summary statistic reporting precision in section 9.1. Added clopper-pearson as the Cl calculation method for PASI and sPGA response rates in section 9.6.2. Added COVID related analyses for the Lead-in Period and COVID-19 SMQ search strategy in section 9.7.1.

Protocol Number: 20200497

Date: 10FEB2023 Page 3 of 36

Protocol Number: 20200497

Date: 10FEB2023 Page

Table of Contents

1.	Intro	duction	8
2.	Obje	ctives, Endpoints and Hypotheses	8
	2.1	Objectives and Endpoints	8
	2.2	Hypotheses and/or Estimations	9
3.	Stud	y Overview	9
	3.1	Study Design	9
	3.2	Sample Size	10
	3.3	Adaptive Design	10
4.	Cova	riates and Subgroups	10
	4.1	Planned Covariates	10
	4.2	Subgroups	11

sPGA	Static Physician's Global Assessment
SAS	Safety Analyses Set

Protocol Number: 20200497

Date: 10FEB2023 Page 8 of 36

 $\begin{array}{lll} \text{SOC} & \text{system organ class} \\ \text{TEAE} & \text{treatment-emergent adverse events} \\ \text{TFL} & \text{Tables, Figures, and Listings} \\ t_{\text{max}} & \text{time of maximum concentration} \\ t_{\text{last}} & \text{time of the last concentration reported} \\ \end{array}$

Protocol Number: 20200497

Date: 10FEB2023 Page 9 of 36

1. Introduction

The purpose of this Statistical Analysis Plan (SAP) is to provide details of the statistical analyses that have been outlined within protocol (No. 20200497) version 1.0 for ABP 501 study 20200497, dated 03 Jun 2021The scope of this plan includes the final analysis that is planned and will be executed by Parexel International, the designated contract research organization.

2. Objectives, Endpoints and Hypotheses

2.1 Objectives and Endpoints

Objectives	Endpoints		
Primary: To demonstrate pharmacokinetic	Primary pharmacokinetic endpoints: • AUC _{tau} between week 28 and week 30		
similarity in subjects with multiple switches between Humira® (adalimumab) and ABP 501 compared	 C_{max} between week 28 and week 30 Secondary pharmacokinetic endpoints: 		
to subjects receiving continued use of Humira	 t_{max} between week 28 and week 30 C_{trough} between week 14 and week 28 		
Secondary:	Secondary Endpoints:		
To assess the efficacy, safety and immunogenicity in subjects with multiple switches between ABP 501 and Humira compared with subjects receiving continued use of Humira	 Efficacy related Endpoints: PASI percent improvement from baseline (day 1) to week 30 PASI 75 response at week 30 PASI 90 response at week 30 PASI 100 response at week 30 		
	 Safety related Endpoints: Treatment-emergent adverse events and serious adverse events, post randomization Events of interest, post randomization 		
	Immunogenicity-related Endpoints: • Incidence of antidrug antibodies, post randomization		

Protocol Number: 20200497

Date: 10FEB2023 Page 10 of 36

Enter Exploratory Objectives Endpoints

2.2 Hypotheses and/or Estimations

The analyses of the primary pharmacokinetic(s) (PK) endpoints will test the following hypotheses for each endpoint:

Null Hypothesis (H₀): The geometric means ratio (GMR) between ABP 501 and Humira is outside a prespecified margin of (0.8, 1.25),

versus

Alternative Hypothesis (H_a): The GMR between ABP 501 and Humira is within a prespecified margin of (0.8, 1.25).

To establish that the risk in terms of safety or diminished efficacy of switching between ABP 501 and Humira is not greater than the risk of using Humira without such switching, both 90% confidence intervals (CIs) of GMR of ABP 501 versus Humira for AUC_{tau} and C_{max} from the primary analysis must fall within the prespecified margin above.

3. Study Overview

3.1 Study Design

This is a randomized, double-blinded, phase 3 study in adult subjects with moderate to severe plaque psoriasis. This study is planned to be conducted globally at study centers including but not limited to North America and Europe.

The total duration of study participation for each subject will be about 36 weeks, with up to 4 weeks for screening and approximately 32 weeks after the first investigational product administration.

Subjects will receive an initial 6 doses of Humira on week 1 (day 1) mg loading dose), 1 week later on week 2 mg), then 2 weeks later on week 4, week 6, week 8, and week 10 mg), administered subcutaneously (SC). At week 12, subjects will be randomized to either the continued use group or switching group in a 1:1 ratio, stratified by geographic region and prior biologic use at baseline (week 1/day 1, yes vs. no). Subjects in the continued use group will stay on Humira Q2W with last dose at week 28 and subjects in the switching group will switch to ABP 501 Q2W at week 12 (dosed week 12 and week 14), then back to Humira Q2W at week 16 (dosed week 16 and week 18), and again to ABP 501 Q2W at week 20, (dosed week 20, week 22, week 24, week 26, and last dose at week 28).

At Week 12, efficacy assessments will be conducted including evaluation of PASI.

Protocol Number: 20200497

Date: 10FEB2023 Page 11 of 36

Subjects who do not achieve a PASI 50 response or better improvement at Week 12 are considered as non-responders and will not be randomized at Week 12; these subjects will complete End of Study (EOS) procedures at Week 12. The Lead-in Period will occur from day 1 until prior to randomization at Week 12. Those unable to complete the Week 12 visit will be discontinued from the study. All enrolled subjects not randomized at Week 12 will be considered lead-in failures and the lead-in failure reason will be documented.

3.2 Sample Size

Approximately 414 subjects will be enrolled to receive Humira during the Lead-in Period. Subjects with prior biologic use for psoriasis will be capped at 50% of the total enrolled subjects. This sample size will ensure approximately 342 subjects will be randomized at Week 12 after the Lead-in Period, considering 17% lead-in failures (including treatment failure defined as subjects who do not achieve PASI 50 response or better improvement at Week 12), in a 1:1 ratio to the continued use group or the switching group. The randomization will be stratified by prior biologic use for psoriasis at baseline (week 1/day 1, yes vs. no) and geographic region. The number of subjects enrolled may be adjusted during the study with the actual lead-in failure rate seen to ensure approximately 342 subjects will be randomized at Week 12. Subjects already enrolled will be allowed to be randomized at Week 12. The sample size of 342 randomized subjects will provide at least 90% power to demonstrate similarity of the primary PK endpoints based on the Two One Sided Tests at a 0.05 significance level, assuming a between-subject variability (as measured by coefficient of variation) of 53% for ABP 501 and Humira, a true GMR of 1 between ABP 501 and Humira , a similarity margin of (0.8, 1.25), and 15% drop outs after randomization through Week 30 (including subjects who discontinue the study prior to Week 28 and those reaching Week 28 but do not have evaluable primary PK endpoints between weeks 28 and 30).

3.3 Adaptive Design

None.

4. Covariates and Subgroups

4.1 Planned Covariates

Unless stated otherwise, the stratification factors (prior biologic use for psoriasis ["yes" versus "no"] at baseline [week 1], and geographic region) will be included as covariates in the statistical models for the PK and efficacy analyses. In addition, weight and PK trough concentration at the end of the Lead-in Period (week 12) will be included as

Protocol Number: 20200497

Date: 10FEB2023 Page 12 of 36

covariates in the statistical model for the primary PK endpoints. For continuous efficacy endpoints (e.g. PASI percent improvement from baseline, Body Surface Area (BSA) change from baseline), in addition to the stratification factors, the corresponding baseline scores will also be included as covariates in models.

Covariate values may be discordant if collected via case report form (CRF) and Interactive Web/Voice Response System (IXRS). Analyses that are intended to evaluate the treatment effect and include stratification variables as covariates in the model will be based on the CRF stratification values, regardless of the subject's IXRS stratification values, to provide unbiased estimates of the effects of treatment and stratification variables without loss of efficiency (Ke et al, 2017).

4.2 Subgroups

Subgroup analyses will be conducted for the primary PK parameter endpoints for the neutralizing antidrug antibody (ADA) negative subgroup (see definition in Section 5.1).

5. Definitions

5.1 General

Actual Treatment Received During Lead-in Period

If a subject received any dose of ABP 501 during the Lead-in Period, the actual treatment for the subject is defined as ABP 501. Otherwise, the actual treatment for the subject is defined as Humira.

Actual Treatment Received During Post-randomization Period

For a subject randomized to switching group or continued use group and receiving all assigned treatments, the actual treatment received is defined as the switching group or the continued use group. Subjects randomized to the switching group that deviate from the switching regimen will be analyzed in a separate group and their actual treatment will be labeled "Deviated from Switching Regimen". Similarly, subjects randomized to the continued use group and deviate from this treatment regimen will be in actual treatment group labeled "Deviated from Continued use Regimen".

Baseline

Unless stated otherwise, the baseline of the study is defined as the last non-missing assessment taken prior to the first dose of investigational product (IP) a subject received (see definition of first dose date). In cases where baseline assessments are taken on the

Protocol Number: 20200497

Date: 10FEB2023 Page 13 of 36

same day as the first dose of IP, and either no times are reported or the IP and assessment times are the same, it will be assumed that these assessments are taken prior to IP being administered.

Change from Baseline

Change from baseline is defined as (value at post-baseline visit – value at baseline).

Concomitant and Prior Medication

Prior medications are defined as medications with a stop date prior to first dose of IP the subject received (see definition of first dose date). Concomitant medications are defined as any medications ongoing at the start of IP treatment for the subject or with a start date on or after the first dose date.

Developing ADA incidence

Developing antibody incidence during the Lead-in Period is defined as the number of subjects in the Lead in Treated Set (LTS) with a negative or no antibody result at baseline and a positive antibody result post-baseline (including unscheduled visits) during the Lead-in Period divided by the number of subjects in the LTS with at least one post-baseline result during the Lead-in Period.

Developing antibody incidence during the Post-randomization Period is defined as the number of subjects in the Safety Analysis Set (SAS) who have a positive result post randomization and have never tested positive (i.e., negative or no results) prior to the first dose of post-randomization IP divided by the number of subjects in the SAS who have at least a result post randomization.

End of Study (EOS) Date

The EOS date is the date recorded on the End of Study page of the CRF.

First Dose Date

It is defined as the date the subject received the first dose of IP.

First Post-randomization Dose Date

It is defined as the date the subject received the first post-randomization dose of IP.

Last Dose Date

It is defined as the date the subject received the last dose of IP.

Last Observation Carried Forward (LOCF)

Protocol Number: 20200497

Date: 10FEB2023 Page 14 of 36

A method of imputation where missing post-baseline data will be imputed by carrying forward the last non-missing post-baseline value for that endpoint. Baseline values will not be carried forward.

Neutralizing ADA Negative Subgroup

Defined as subjects in the subset of Safety Analysis Set (SAS) who have never tested positive (i.e. tested negative or no results) prior to the first dose of post-randomization IP, have at least one neutralizing ADA result post-randomization, and all available post-randomization neutralizing ADA results are negative.

Non Responder Imputation (NRI)

A method of imputation where a subject with missing post-baseline binary response data will be imputed as a non-responder, regardless of the reasons for missing data.

Study Analysis Visit

If more than one actual visit (including the unscheduled visits) falls within the same defined window, the visit closest to the target day with non-missing data will be considered for analysis. If two actual visit dates are at the same distance from the target day, the later visit with non-missing data will be considered for analysis.

For Efficacy, Vital, Safety Lab & PK

					Endpoint	
Study Analysis Visit	Target Day	Study Day	Interval (days)	Efficacy	Vital & Safety Labª	PK
Baseline ^b	1	≤1	NA	Х	Х	Х
Week 2	8	2-21	20		X	
Week 6	36	22-56	35	Χ	X	Χ
Week 12 ^b	78	57-91	35	Χ	X	Χ
Week 16	106	92-119	28	Χ	X	Χ
Week 20	134	120-161	42	Χ	X	Χ
Week 28	190	162-196	35		X	Χ
Week 30	14 days post week 28 dose	197-210	14	Х	Х	
Week 32	218	≥211	NA		Χ	

^a Safety lab is not scheduled at week 2 and week 16. Laboratory parameters assessment will not be included at these two visits in the output tables.

^b If a subject has laboratory measurements on the same day as the first dose date at week 1/Day 1 or week 12 but at a time after the first dose of IP at week 1/Day 1 or week 12, respectively is administered, the laboratory measurements will not be defined as baseline or week 12, but will be included in consideration for week 6 or 20 measurements, respectively.

Protocol Number: 20200497

Date: 10FEB2023 Page 15 of 36

PK concentrations between Week 28 – Week 30 are summarized by nominal study visit per the following table as listed in the protocol:

Tolerance Windows for Pharmacokinetic Endpoint Sample Collection

Study Visit	Tolerance Windows ^a
Week 28 predose	Within 3 hours prior to week 28 investigational product administration
1 hour post week 28 dose	±15 minutes
1 day post week 28 dose	±5 hours
3 days post week 28 dose	±6 hours
4 days post week 28 dose	±6 hours
7 days post week 28 dose	±6 hours
11 days post week 28 dose	±24 hours
14 days post week 28 dose	±48 hours

^a The week 28 visit and dose should be performed with a window of \pm 3 days. Subsequent visits are done in relation to the actual week 28 investigational product dose date (eg, for the 3 days post week 28 dose timepoint, the PK sample should be collected 3 days after the actual week 28 dose, with a collection window of \pm 6 hours). PK: pharmacokinetic(s)

For ADA

Study Analysis Visit	Target Day	Study Day
Baseline	1	<=1
Week 6	36	<=56
Week 12	78	<=91
Week 16	106	<=119
Week 20	134	<=161
Week 28	190	<=196
Week 30	14 days post week 28 dose	<=210
Week 32	218	<=EOS Visit Date

Study Day

Study day is defined as the number of days from Study Day 1.

Before Study Day 1: Study Day = (Date of assessment – Date of Study Day 1)

Protocol Number: 20200497

Date: 10FEB2023 Page 16 of 36

On or After Study Day 1: Study Day = (Date of assessment – Date of Study Day 1) +1

Therefore, the day prior to Study Day 1 is -1.

Study Day 1

Study day 1 is defined as the first day of IP the subject received (see definition of first

dose date).

Study Period

The following definitions will be used for PK, safety and efficacy analyses.

Lead-in Period

It is defined as the time period from the first dose of IP the subject received (see

definition of first dose date for the subject) until prior to the first post-randomization dose

for subjects who are randomized and treated post-randomization, or to the EOS visit for

subjects not randomized or for subjects who were randomized but not treated post-

randomization.

Post-randomization Period

For subjects who are randomized and treated post-randomization, it is defined as the

time period from the first post-randomization dose to the EOS visit.

Study Randomization

Study randomization is defined as when subject receives a random treatment allocation

via the IXRS system.

Total IP Exposure Duration

The total IP exposure duration for the subject (in weeks) for each study period (Lead-in

Period, Post-randomization Period) will be derived as: (the period end date - the period

start date+1)/7. The Lead-in Period end date for the subjects who are randomized and

treated post-randomization is the date of the first IP post randomization -1.

Transient ADA

A transient ADA result during the Lead-in Period is defined as a positive antibody result

post-baseline (including unscheduled visits) during the Lead-in Period with a negative or

no antibody result at baseline and a negative result at the subject's last visit tested within

the Lead-in Period.

Protocol Number: 20200497

Date: 10FEB2023 Page 17 of 36

A transient ADA result during the Post-randomization Period is defined as a positive antibody result post-randomization (including unscheduled visits) during the Post-randomization Period with negative or no antibody results prior to the first dose of post-randomization IP and a negative result at the subject's last visit tested within the Post-randomization Period.

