9.4 Populations for Analysis

For purposes of analysis, the following analysis sets are defined in Table 9-1. The Full Analysis Set will be analyzed according to the treatment that the subject is randomized to (regardless of actual treatment received). For all other parameter sets, subjects will be analyzed according to the investigational product they actually received. A precise definition of "as actually received" will be added in the SAP.

Clinical Study Protocol: 20200497

Final 1.0 Date: 03 Jun 2021 Page **61** of **87**

Table 9-1. Populations for Analysis

Population (Analysis Set)	Description	
Lead-in Treated Set	The Lead-in Treated Set consists of all enrolled subjects treated with at least 1 dose of investigational drug during the lead-in period.	
Full Analysis Set	The Full Analysis Set consists of all randomized subjects (randomization occurs at week 12).	
Safety Analysis Set	The Safety Analysis Set consists of all randomized subjects who received at least 1 dose of investigational product post randomization.	
PK Concentration Analysis Set	The PK Concentration Analysis Set which will include all randomized subjects who received at least 1 dose of investigational product post randomization and have at least 1 reported serum concentration of ABP 501 or adalimumab.	
PK Parameter Analysis Set	The PK Parameter Analysis Set consists of all subjects who are randomized and received all assigned doses post-randomization and who have an evaluable ABP 501 or adalimumab serum concentration-time profile between weeks 28 and 30	
Per Protocol PK Parameter Analysis Set	The Per Protocol PK Parameter Analysis Set consists of all subjects in the PK Parameter Analysis Set who do not have an important protocol deviation that could affect the primary PK endpoints.	
Per Protocol Efficacy Analysis Set	The Per Protocol Efficacy Analysis Set will include all subjects who are randomized and received all assigned doses post-randomization and who have not experienced an important protocol deviation that may affect the evaluation of the efficacy endpoints.	

PASI = Psoriasis Area and Severity Index; PK = pharmacokinetic(s); SAP = statistical analysis plan.

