9.5.3 Safety Endpoints

All reported adverse events will be categorized by system organ class and preferred term according to the Medical Dictionary for Regulatory Activities (latest version at the time of final analysis) dictionary and graded by CTCAE, version 4.03.

Safety analyses of the safety endpoints will be performed based on the Safety Analysis Set according to the actual treatment groups (switching group versus continued-use group). Treatment-emergent adverse events post randomization are defined as adverse events that start or worsen on or after the first dose of investigational product post randomization and prior to the EOS. The numbers and percentages of subjects reporting treatment-emergent adverse events, serious adverse events and events of interests will be tabulated by treatment group. The number and percent of subjects developing binding or neutralizing antidrug antibody (ADA) in the subset of Safety Analysis Set who have at least one ADA result post randomization will be tabulated descriptively by treatment group and by visit.

Laboratory data (hematology, serum chemistry, and urinalysis) will be converted to Système International units for reporting purposes. Absolute values and changes from week 12 for laboratory data post randomization will be summarized descriptively by treatment group and visit.

For vital signs post randomization, absolute values, and changes from week 12 will be summarized descriptively by treatment group and visit.

Physical examination values post randomization will be summarized descriptively by treatment group and by visit.

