6.2 Safety Analysis Set

The Safety Analysis Set (SAS) consists of all randomized subjects who received at least 1 dose of IP post-randomization. This analysis set will be used for analyses of the safety endpoints during the Post-randomization Period according to actual treatment received.

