6.5 Per-protocol Efficacy Analyses Set

The Per-protocol Efficacy Analysis Set consists of all subjects who are randomized and receive all assigned doses post-randomization and who have not experienced an important protocol deviation that may affect the evaluation of the efficacy endpoints. This analysis set will be used for primary analysis of the secondary efficacy endpoints and will be analyzed according to actual treatment received.

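### SAP 5.1 does not say whether a missed or stopped dose takes a subject out of the switching or continued-use group; read literally it does, which conflicts with the widened PK Parameter Analysis Set and moves early stoppers out of the main safety and ADA columns

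*SAP*

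**What the plan says.** Protocol 9.4 sets the principle. In every set other than the Full Analysis Set, "subjects will be analyzed according to the investigational product they actually received". It leaves the detail for later: "A precise definition of 'as actually received' will be added in the SAP".

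SAP 5.1 is where that definition appears. For a subject randomized to either group "and receiving all assigned treatments, the actual treatment received is defined as the switching group or the continued use group". It continues: "Subjects randomized to the switching group that deviate from the switching regimen will be analyzed in a separate group". The continued-use arm has a parallel rule, and each deviating group carries a label naming its arm. The word *deviate* is not defined, and no other section says whether a missed, delayed or stopped dose is meant. For the lead-in period, 5.1 uses a rule based on product: "If a subject received any dose of ABP 501 during the Lead-in Period, the actual treatment for the subject is defined as ABP 501".

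These labels decide who is compared:

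- **Primary PK.** SAP 9.5.1.1 contrasts the switching and continued-use groups by actual treatment in the PK Parameter Analysis Set. SAP 6.3 now admits to that set anyone with at least one post-randomization dose and an evaluable week 28 to 30 profile. Section 10 explains that the protocol's all-doses condition might exclude evaluable subjects.
- **Safety.** Protocol 9.5.3 says the analyses "will be performed based on the Safety Analysis Set according to the actual treatment groups (switching group versus continued-use group"). SAP 6.2 says: "This analysis set will be used for analyses of the safety endpoints during the Post-randomization Period according to actual treatment received".
- **ADA.** SAP 9.7.6 tabulates by treatment group and visit in the same set.
- **Efficacy.** SAP 6.5 uses different wording: "The Per-protocol Efficacy Analysis Set consists of all subjects who are randomized and receive all assigned doses post-randomization".

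**The concern.** The protocol expects the cases that 5.1 leaves open. The Table 1-1 footnotes and Protocol 6.7 say how dosing resumes after a delayed or missed dose. Protocol 7.1 recommends that subjects who stop product remain in the study for safety surveillance. The rule will therefore have to be applied to real subjects, and two programmers could derive different groups from the same text.

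The most literal reading treats the two categories in 5.1 as complements: a subject either received everything assigned or deviated. Membership of the two main groups then depends on what happened after randomization. For PK, the contrast loses the very subjects that Section 10 set out to admit. For safety and ADA, the two main columns lose subjects who stopped product before week 28, including those who stopped because of an adverse event. That is an awkward selection in a study meant to show that switching carries no greater risk than staying on the reference product.

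**Working it through.** **1. The two readings side by side.**

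| Subject | Dose-based reading (literal) | Product-based reading |
|---|---|---|
| Misses one dose between weeks 12 and 26, dosed at week 28, evaluable profile | In the PK Parameter Analysis Set (SAP 6.3), but in a deviated group and so outside the 9.5.1.1 contrast | In the assigned group and in the contrast |
| Stops product before week 28, for example for an adverse event | In the Safety Analysis Set, but outside both main safety and ADA columns | In the assigned group |
| Receives the wrong product or sequence | Deviated group | Deviated group |

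For primary PK only the first row matters in practice. A subject who stopped before week 28 would normally have no evaluable week 28 to 30 profile on any reading.

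**2. Which reading the text supports.** The structure of 5.1 points to the dose-based reading. Four places point to the product-based one: the product wording of Protocol 9.4, the product-based lead-in rule in 5.1, the choice of *doses* in SAP 6.5 against *treatments* in 5.1, and the purpose stated in SAP Section 10. None of them settles it.

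**3. Whether another planned analysis covers the gap.** The Per-protocol PK analysis (SAP 6.3) uses actual treatment. The gender-adjusted repeat (9.5.1.2) and the neutralizing-ADA-negative subgroup (9.5.4) reuse the primary model. Only efficacy has a model by randomized group (9.6.2.2). No adverse event or ADA table by randomized arm is planned.

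**4. The plan's power figure.** Inputs from Protocol 9.3 and SAP 3.2: 342 randomized 1:1, 15% drop-out, CV 53%, true ratio 1, margin 0.8 to 1.25, two one-sided tests at 0.05.

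- Evaluable: 342 × 0.85 = 290.7, about 145 per arm.
- Log-scale SD: √ln(1 + 0.53²) = 0.498.
- SE: 0.498 × √(2/145) = 0.0584.
- Normal approximation: 2Φ(0.2231/0.0584 − 1.645) − 1 = 97.0%. The t-based calculation also gives 97.0%.

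The stated figure of at least 90% is met for each endpoint.

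**5. Illustration under the dose-based reading only.** The documents give no missed-dose rate. The per-dose rates q below, and independence between doses, are assumptions. Nine doses follow randomization. An evaluable profile is taken to need the week 28 dose, so eight earlier doses count. The share with at least one miss is 1 − (1 − q)⁸.

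| Assumed q | Share with a miss | Of 290 evaluable | Left per arm | Power per endpoint |
|---|---|---|---|---|
| 0 | 0% | 0 | 145 | 97.0% |
| 1% | 7.7% | 22 | 134 | 95.6% |
| 2% | 14.9% | 43 | 123 | 93.8% |
| 3% | 21.6% | 63 | 114 | 91.7% |

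Protocol 9.2 requires both endpoints to succeed. If they were independent, joint power would go from 0.970² = 94.0% to 0.917² = 84.0%. AUC and Cmax come from the same profile, so independence is probably pessimistic. Under the product-based reading, missed doses cause no loss.

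**The case against.** The strongest reply is that the product-based reading is the intended one. Section 10 would make little sense otherwise, and one clarifying sentence would be enough. The point about intent is fair, which is why this is an inconsistency and not a demonstrated error. But 5.1 as written supports the other reading at least as well, and it is the rule that will be programmed.

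Second, the worst case for PK is essentially the protocol's own PK Parameter Analysis Set: all doses received and an evaluable profile. An evaluable profile is a post-randomization condition on either reading. Both statements are true. Yet the SAP has declared the protocol's set possibly too restrictive and replaced it, so returning to it through a labelling rule would not be a deliberate choice.

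Third, stopping because of harm is not hidden. SAP 9.2 summarizes discontinuation with reasons and lists discontinued subjects for the Full Analysis Set. SAP 9.3 tabulates important deviations by randomized group. SAP 9.7.1 lists serious events. The deviated groups carry arm labels, so columns can be added together. Safety and immunogenicity are descriptive (Protocol 2.1). All of this limits the harm. It does not replace adverse event and ADA tables by arm.

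A reader might also infer more than the documents support:

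- **That the rule treats the arms differently,** because an early stopper in the switching arm never makes the third switch. SAP 5.1 applies the same rule to both arms, and the continued-use regimen also runs to week 28, so an early stopper there falls short too.
- **That the groups in the primary contrast are unspecified.** SAP 9.5.1.1 names them. What is open is who carries the labels.
- **That some subjects have no group at all.** This requires breaking the complement that 5.1 appears to intend.

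**Conclusion.** The point holds as an internal inconsistency that should be resolved before unblinding. SAP 5.1 does not deliver the precise definition that Protocol 9.4 promised. Its literal reading contradicts the reason for the change in Section 10, and it would move early stoppers out of the two main safety and ADA columns.

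The size cannot be derived from the documents. The 22 to 63 subjects in the PK illustration depend on assumed miss rates, on independence between doses, and on the reading that other passages disfavour. The number of early stoppers affected in the safety tables is unknown. A reader might take this as a threat to power, but per-endpoint power stays above 91% across the assumed range. The issue is who is compared and whether that was fixed in advance. The primary efficacy analysis is little affected, because its set requires all assigned doses in any case.

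**What to change.** Before unblinding:

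1. State in SAP 5.1 that a missed, delayed or stopped dose does not change a subject's analysis group for the Safety, ADA, PK Concentration and PK Parameter analyses. Limit the two deviated groups to receipt of the wrong product or the wrong sequence.
2. Add the key safety tables, including the event-of-interest risk differences of SAP 9.7.1, and the ADA tables by randomized arm, so that wrong-product subjects are also counted in a comparison by arm.

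The cost is SAP wording, one derived variable and a few extra tables. No protocol amendment is needed, since Protocol 9.4 assigns this definition to the SAP. The downside is that some profiles with an earlier missed dose enter the primary PK analysis, which is what Section 10 already intends.
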